Targeted Variable	General population	At risk - other	At risk: lung-specific	At risk: heart-specific	At-risk: combo
Response efficacy	Taking a side street route cuts a person's exposure to air pollution by half	Taking a side street route cuts a person's exposure to air pollution by half	Taking a side street route cuts a person's exposure to air pollution by half	Taking a side street route cuts a person's exposure to air pollution by half	Taking a side street route cuts a person's exposure to air pollution by half
			If you have a preventer inhaler, using it every day will reduce the inflammation that causes asthma. Your reliever inhaler will help to ease symptoms straight away.		If you have a preventer inhaler, using it every day will reduce the inflammation that causes asthma. Your reliever inhaler will help to ease symptoms straight away.
Response costs (i.e. negative consequences associated with the recommended behaviour)	The CityAir App can help you find side street routes, which do not necessarily add to your total travel time, and may give you a more pleasant journey.	The CityAir App can help you find side street routes, which do not necessarily add to your total travel time, and may give you a more pleasant journey.	The CityAir App can help you find side street routes, which do not necessarily add to your total travel time, and may give you a more pleasant journey.	The CityAir App can help you find side street routes, which do not necessarily add to your total travel time, and may give you a more pleasant journey.	The CityAir App can help you find side street routes, which do not necessarily add to your total travel time, and may give you a more pleasant journey.

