5.6 MEASURES

Table 4. Summary of measures.

Timing	Measure	How it will be measured
First Online Questionnaire – After reading hypothetical high air pollution scenario	Baseline intentions ^a to adopt protective behaviours in response to hypothetical, high air pollution alert	Assuming the situation described was happening right now, how much would you agree with the following statements? 
 - I intend to follow the recommendations received with the air alert to reduce exposure to air pollution - I will avoid going outdoors - I intend to reduce length or level of my physical activity outdoors - I intend to change my travel route - I intend to change my exercise location - I intend to change the time when I travel - I intend to change the time when I exercise outdoors
	Baseline medication adherence intentions ^a	If you have lung problems: 
 - I intend to use my preventer inhaler daily - I intend to carry my reliever inhaler with me
	Other baseline intention ^a (not advised behaviours)	
 - I will wear a mask as a protection from air pollution - I intend to reduce length or level of my physical exercise indoors
	Previous protective behaviour ^b	- In the past 4 weeks, how often have you taken action to reduce exposure to air pollution, I response to hearing or reading an air quality forecast?
	Planning	
 - In the last 4 weeks, to reduce your exposure to air pollution, have you considered making permanent changes to your daily travel route or exercise place and time?^c - In the last 4 weeks, how often have you checked air quality information before doing physical activity outdoors?^b
	Physical activity ^d	- To stay healthy, the NHS recommends at least 150 minutes of moderate physical activity (e.g. cycling, fast walking, swimming) every week (e.g. 30 minutes 5 days a week). Based on this, how physically active were you in the last week?
	Symptoms ^c	- Have you ever experienced symptoms caused by air pollution?
Air Alert period – Online questionnaires	Alert recall ^e	- Recently we sent you an air quality alert about poor air quality. What was the level of air pollution reported?

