	Actual Behaviour change ^c	In response to receiving the air quality alert: 
 - I reduced length or level of my physical activity outdoors - I changed my travel route - I changed my exercise location - I changed the time when I travelled - I changed the time when I exercised outdoors - If you answered no, please report the reasons [text box].
	Medication adherence ^c	If you have lung problems: 
 - I used my preventer inhaler daily - I carried my reliever inhaler with me when going outdoors. - If you answered no, please report the reasons [text box].
Final Online Questionnaire – at 4 weeks	Behaviour change at 4 weeks ^b	- In the past 4 weeks, how often have you taken action to reduce exposure to air pollution, I response to hearing or reading an air quality forecast?
	Physical activity ^d	- To stay healthy, the NHS recommends at least 150 minutes of moderate physical activity (e.g. cycling, fast walking, swimming) every week (e.g. 30 minutes 5 days a week). Based on this, how physically active were you in the last week? ^e
	Action planning	
 - In the last 4 weeks, to reduce your exposure to air pollution, have you considered making permanent changes to your daily travel route or exercise place and time?^c - In the last 4 weeks, how often have you checked air quality information before doing physical activity outdoors?^b
	Worry ^a	Adapted from Witte et al. (34) 
 - The information received through the CityAir app made me worry about the possibility of suffering health effects from exposure to air pollution

	- The information received through the CityAir app made me nervous and tense about the possibility of suffering health effects from exposure to air pollution
Severity ^a	Adapted from Witte et al. (34)
	- Air pollution is a severe threat to my health
Conditional susceptibility ^f	- How likely do you think you are to suffer from health effects due to air pollution if you do not take any action to reduce exposure? - How likely do you think people of your same age and sex are to suffer from health effects due to air pollution if they do not take any action to reduce exposure?
Response efficacy ^a	Adapted from Witte et al. (34)
	- Following the health advice received through the CityAir app is effective in protecting me from exposure to air pollution

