Medication response efficacy ^a	If you have lung problems: - Taking my preventer medications daily is effective in helping me to control my asthma - Carrying my reliever medication with me is an effective way to protect my health
Self-efficacy ^a	Items adapted from Witte et al (34) and Rhode et al (35)
	- I am confident I would be able to follow the health advice received through the CityAir app, if I wanted to
Medication self-efficacy ^a	Items adapted from Witte et al (34) and Rhode et al (35)
	- If you have lung problems: I am confident I would be able to take my preventer inhaler every day , if I wanted to - I am confident I would be able to remember to carry my reliever inhaler with me during days of poor air quality, if I wanted to
Response costs ^a	- I do not have enough time to follow the health advice received through the CityAir app - Taking side roads makes my journey too long
Medication response costs ^a	If you have lung problems: - Using the preventer inhaler daily is not safe - Using the preventer inhaler daily makes me dependent on it
Unwanted consequences of intervention ^a	- In the last 4 weeks I stopped exercising altogether due to receiving alerts about poor air quality - In the last 4 weeks, I made an emergency /unplanned visit to A&E or visited my GP due to symptoms caused by air pollution
Sensory cue prevalence ^a	- I trust my own perception of air quality more than any official air quality alert
Credibility ^g	- Meyer's credibility index (36,37) (α=.67)
Clarity ^h	- Overall, how clear were the messages received?
Perceived informed choice ^a	- I received enough information to make an informed choice on how to reduce my exposure to air pollution
Intentions ^a to adopt protective behaviour in response to hypothetical, high air pollution alert	[After reading again the high air pollution hypothetical scenario and tailored advice] - I intend to follow the recommendations received with the air alert to reduce exposure to air pollution - I will avoid going outdoors - I intend to reduce length or level of my physical activity outdoors - I intend to change my travel route - I intend to change my exercise location - I intend to change the time when I travel - I intend to change the time when I exercise outdoors

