Medication adherence intentions ^a	If you have lung problems: - I intend to use my preventer inhaler daily - I intend to carry my reliever inhaler with me
Other intentions (not advised behaviours) ^a	- I will wear a mask as a protection from air pollution - I intend to reduce length or level of my physical exercise indoors

Notes: ^a Measured on 9-point scales, where 1=strongly disagree to 9=strongly agree; ^b From 1 Not at all to 9 all of the time; ^c Possible answers: yes, no, not sure; ^d From 1 Not at all, to 7 more than 150 minutes; ^e Possible answers: Low, Moderate, High, Very High, Not sure, I did not receive any alert; ^f From 1=not at all likely to 9=extremely likely; ^g on a 5-point scale; ^h 1= not clear at all to 9= extremely clear. Demographic data will be collected for all the participants in the first questionnaire.

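### Actual inhaler use, which the enhanced messages target, is asked only after an alert, with no baseline or week-4 item and no answer for people without the inhaler

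*Combined protocol and SAP*

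**What the plan says.** **The target.** Table 3 (section 5.5) gives intervention participants in the lung-specific and combined columns messages on the benefit and safety of daily preventer use. One begins "If you have a preventer inhaler, using it every day will reduce the inflammation that causes asthma". The table does not tie these messages to a pollution level, and the wording accepts that some recipients have no preventer.

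**First questionnaire (Table 4, section 5.6).** Lung participants state intentions, for example "I intend to use my preventer inhaler daily". The only past-behaviour item on protective action asks "how often have you taken action to reduce exposure to air pollution" over the past 4 weeks. It does not mention inhalers.

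**Alert-period questionnaire.** A separate medication adherence row, for people with lung problems, has two items: "I used my preventer inhaler daily" and "I carried my reliever inhaler with me when going outdoors". The answer options are given in note c: "Possible answers: yes, no, not sure". A free-text prompt follows: "If you answered no, please report the reasons [text box".

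**Final questionnaire.** Lung participants are asked about response efficacy (for example "Taking my preventer medications daily is effective in helping me to control my asthma"), self-efficacy, costs and intentions. No item asks about use. The behaviour item is the same general 4-week frequency question as at baseline.

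**Analysis (section 6.1).** Chi-square tests compare the arms on self-reported behaviour change after a real moderate episode. Inhaler use is not named.

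**Appendix 1.** A row for actual adherence is ticked at Weeks 1 to 3 and at Week 4, but not at baseline. Its content is not defined.

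**The concern.** Daily preventer use is a standing habit, so it suits a before-and-after question. The plan uses that design for exposure-reducing action, with the same 4-week item at baseline and week 4, but not for inhaler use. Three consequences follow.

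- The use outcome depends on an alert. Section 4, question 3, treats a real alert as something that may or may not occur. Without one, the trial learns what lung participants intend and believe about inhalers, but not what they did.
- With an alert, the yes answers combine people who already used the preventer daily with people who started. The item has no reference period, and there is no earlier answer to set it against.
- The items go to everyone with lung problems. Someone without a preventer must choose no or not sure, or skip the item.

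At stake is whether the trial can say anything useful about behaviour for this part of the intervention. The outcomes for exposure-reducing behaviour are not affected.

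**Working it through.** The plan gives no figure for inhaler use, for the share of participants with lung disease or for inhaler ownership, so there is nothing to reproduce on this point. The first step is a reading of Table 4. The others are illustrations on stated assumptions.

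**1. What is asked, and when**

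| | First questionnaire | After an alert | Week 4 |
|---|---|---|---|
| Inhaler intentions | yes | no | yes |
| Inhaler efficacy, self-efficacy, costs | no | no | yes |
| Actual inhaler use | no | yes | no |
| General exposure-reducing action, past 4 weeks | yes | no | yes |

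**2. Why one post-alert answer cannot show within-person change.** Suppose 60% answer yes after an alert. Change = 60 minus prior use. With prior use of 30%, 50% or 70%, the change is +30, +10 or −10 points. One observed figure fits all three.

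**3. Habitual users and room to improve.** Suppose 50% of owners already use the preventer daily. With no message effect, about 50% of owners in each arm answer yes. To reach 70% in the intervention arm, the messages must convert 20/50 = 40% of the owners who were not daily users.

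**4. Dilution by non-owners.** Let *w* be the share of lung respondents who own a preventer, and let all non-owners answer no. Observed difference = *w* × true difference among owners. With a true difference of 20 points (50% against 70%):

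| Ownership *w* | Observed rates | Difference |
|---|---|---|
| 100% | 50% v 70% | 20 points |
| 80% | 40% v 56% | 16 points |
| 70% | 35% v 49% | 14 points |
| 60% | 30% v 42% | 12 points |

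**5. Precision of the post-alert comparison.** Assumptions: two-sided α = 0.05, equal arms (the ratio is not stated), and 240/1.2 = 200 completers who all receive and answer an alert questionnaire.

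Sample size per arm = [1.96√(2p̄(1−p̄)) + 0.8416√(p₁(1−p₁)+p₂(1−p₂))]² / (p₂−p₁)².

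- Full ownership, 50% v 70%: (1.96√0.48 + 0.8416√0.46)²/0.04 = (1.358 + 0.571)²/0.04 = 93 per arm for 80% power.
- 70% ownership, 35% v 49%: 194 per arm.

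Power = Φ{[Δ − 1.96√(2p̄(1−p̄)/n)] / √[(p₁(1−p₁)+p₂(1−p₂))/n]}, where n = 200 × lung share / 2. For a 50% lung share, n = 50: (0.20 − 1.96 × 0.0980)/0.0959 = 0.083, and Φ(0.083) = 53%.

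| Lung share | n per arm | Power, all own | Power, 70% own |
|---|---|---|---|
| 10% | 10 | 14% | 9% |
| 20% | 20 | 25% | 14% |
| 30% | 30 | 35% | 19% |
| 50% | 50 | 53% | 29% |

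The comparison is weak even with full ownership, and dilution weakens it further.

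**The case against.** The strongest reply is that the trial is randomised (section 5.1). A difference between arms in post-alert use estimates the message effect without any baseline. Habitual users are balanced between arms in expectation, so they cost precision and do not cause bias. This stands. A reader might infer that the trial cannot show any effect on inhaler use at all, and the documents do not support that.

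Four further replies:

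- *The row is labelled adherence, not change.* This is correct. The lead-in tying answers to the alert belongs to the behaviour-change row above. The inhaler items have their own lead-in, for people with lung problems. A long-standing daily user who answers yes is correctly counted as adherent. The item is not misworded for adherence; it lacks a reference period and a baseline counterpart.
- *Non-owners can say so in the text box.* Some can, and section 6.2 plans a content analysis of qualitative data. The box does not cover those who answer not sure or leave it blank, and no rule says how such reasons would recode the answer. The 16 to 12 points therefore describe the case in which the box is not used.
- *Intentions are measured twice.* They are, and section 6.1 covers all intention measures by ANCOVA. The inhaler messages do have an outcome without an alert, but it is intention, not use.
- *Appendix 1 ticks actual adherence at Week 4.* The row is undefined. If it includes medication, it conflicts with Table 4. If it means only the general behaviour item, the gap remains.

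Inhaler use is also not named in any research question and concerns a subgroup, so the point should not be ranked with the primary outcomes.

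**Conclusion.** The point holds within limits. On Table 4, actual inhaler use is measured only after an alert. Without one there are no use data. With one, a valid but imprecise between-arm comparison remains, and three things are lost: within-person change, baseline adjustment, and a clean separation of owners from non-owners.

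The size rests on assumptions, since the documents give no rates. At 80% to 60% ownership, with every non-owner answering no, a 20-point effect appears as 16 to 12 points. For 50% against 70% use among owners, power runs from 14% to 53% as the lung share rises from 10% to 50% with full ownership, and from 9% to 29% at 70% ownership.

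This is a cheap improvement to a secondary question. It does not threaten the trial's main comparisons.

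**What to change.** For participants with lung problems:

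1. Add the two use items (preventer used daily; reliever carried), worded for the past 4 weeks, to the first questionnaire and to the final one. In the first, place them before the scenario and advice are shown, so that the messages cannot influence the baseline answers.
2. Add the answer *I do not have this inhaler* to these items in both questionnaires and in the alert questionnaire.
3. State in section 6.1 that week-4 use will be compared between arms among those who report having the inhaler at baseline, adjusted for baseline use. Label this a secondary analysis likely to have low power.
4. Define the actual adherence row in Appendix 1 and reconcile its Week 4 tick with Table 4.

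The cost is two short items in each of two existing online questionnaires, for the lung subgroup only, plus one answer option. The downside is slight extra burden and a possible small reminder effect, similar in both arms. In return the trial gains a use outcome that does not depend on an alert, baseline adjustment, and removal of the dilution from non-owners. The change will not by itself bring a small lung subgroup to adequate power.

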Moderate 4-6	Enjoy your activities as usual ^a	Adults and children with lung problems, and adults with heart problems, who experience symptoms, should consider reducing strenuous physical activity, particularly outdoors. ^b	
Enjoy your activities as usual. However, if you wanted you, you can reduce your exposure to pollution by reducing levels and length of physical activity outdoors.
 
You can also consider changing:
 
 • Travel route or • Exercise location (e.g. use our app to find less polluted roads or parks) or • Time (e.g. mornings or less polluted times). ^e 	
Adults and children with lung problems, adults with heart problems, and older people, should reduce levels and length of physical activity outdoors.
 
Where possible, change:
 
 • Travel route or • Exercise location (e.g. use our app to find less polluted roads or parks) or • Time (e.g. mornings or less polluted times). ^h
High 7-9	Anyone experiencing discomfort such as sore eyes, cough or sore throat should consider reducing activity, particularly outdoors. ^c	Adults and children with lung problems, and adults with heart problems, should reduce strenuous physical exertion, particularly outdoors, and particularly if they experience symptoms. People with asthma may find they need to use their reliever inhaler more often. Older people should also reduce physical exertion. ^d	
Anyone who experiences sore eyes, cough or sore throat should consider limiting their exposure to air pollutants.
 
To do this, you don't need to stay indoors, instead you can reduce levels and length of physical activity outdoors.
 
You can also consider changing:
 
 • Travel route or • Exercise location (e.g. use our app to find less polluted roads or parks) or 	
Adults and children with lung problems, adults with heart problems, and older people, should reduce levels and length of physical activity outdoors.
 
People with asthma may find they need to use their reliever inhaler more often.
 
Where possible, change:
 
 • Travel route or • Exercise location (e.g. use our app to find less polluted roads or parks) or

SHORT TITLE/ACRONYM: Improving the health impact of air quality alerts v.3

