6. STATISTICAL ANALYSES

6.1 Quantitative data

ANCOVAs will be performed for all the intentions measures in relation to the high air pollution hypothetical scenario, adjusting for baseline measures collected about one month earlier (target population and intervention/control group entered as fixed factors). Both main and interaction effects will be tested. ANCOVAs will also be performed for the actual behaviour change at 4 weeks (with the intervention/control group entered as fixed factor). These latter analyses will also be ran in the subgroups of healthy and at-risk participants. Chi square tests will be performed to analyse differences in proportion of self-reported actual behaviour change between groups, in relation to a real moderate air pollution episode. A two-way MANOVA (1000 bootstraps) will test whether there are differences between groups (both main effects and interactions) in perceived susceptibility, worry, severity, perceived response efficacy, perception of time, self-efficacy, trust, clarity, credibility and perceived informed choice measures. Multiple linear regressions will be used to assess the associations between main predictor variables and self-reported behaviour change at 4 weeks. Mediations effects of predictor variables on significant behavioural changes will be tested using PROCESS macro (38).

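### The only graded measure of activity amount covers one week, is capped at 150 minutes and has no planned between-arm analysis, so partial loss of exercise is poorly captured

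*Combined protocol and SAP*

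**What the plan says.** Table 4 (section 5.6) includes a physical activity item in the first questionnaire and again in the one headed "Final Online Questionnaire – at 4 weeks". It opens with "To stay healthy, the NHS recommends at least 150 minutes of moderate physical activity" and then asks "Based on this, how physically active were you in the last week". The table notes give the scale as "From 1 Not at all, to 7 more than 150 minutes".

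Three other items in Table 4 bear on reduced activity:

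- Under unwanted consequences, in the final questionnaire, on a 9-point agreement scale: "In the last 4 weeks I stopped exercising altogether due to receiving alerts about poor air quality".
- In the alert-period questionnaires, under actual behaviour change, answered yes, no or not sure: "I reduced length or level of my physical activity outdoors".
- In both main questionnaires, among behaviours that are not advised, an intention to cut back indoor exercise in the hypothetical scenario.

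In Table 2 (section 5.5), the enhanced Moderate message for the general public says "you can reduce your exposure to pollution by reducing levels and length of physical activity outdoors". The usual message in that cell only tells people to carry on as normal. Section 5.4.1 adds that the study version of the app will send Moderate alerts to the general population, which the ordinary app does not do.

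Section 6.1 begins "ANCOVAs will be performed for all the intentions measures in relation to the high air pollution hypothetical scenario". It goes on to ANCOVAs of behaviour change at 4 weeks, chi-square tests of self-reported behaviour change in a real moderate episode, a MANOVA of listed perceptions, regressions and mediation. It names neither the physical activity item nor the unwanted-consequences items.

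**The concern.** In five of the six enhanced cells of Table 2 the advice is to reduce, or consider reducing, the level and length of activity or exertion. In the sixth (at risk, Very high) it is to avoid intense activity. Exercise may therefore fall as a side effect of the intervention. The protocol accepts this possibility, because it lists stopping exercise as an unwanted consequence and reducing indoor exercise as a behaviour that is not advised.

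To show whether protective behaviour was gained at the price of less exercise, the trial needs a measure of amount that registers partial reductions, and a planned comparison between arms. The one graded measure of amount has a short window and a ceiling, and no comparison is planned. The trial could report more protective behaviour in the enhanced arm and say little about its cost in activity.

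**Working it through.** The plan gives no figure for detectable or expected loss of activity, so there is none to reproduce. The check sets the items side by side and then examines the window and the cap.

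**1. What each item can show**

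| Item (Table 4) | Recall | Scale | Cannot show | Between-arm analysis in 6.1 |
|---|---|---|---|---|
| Physical activity, first and final questionnaires | last week | 1 to 7, top point above 150 min | earlier dips that have recovered; changes above 150 min | none named |
| Stopped exercising because of alerts, final questionnaire | 4 weeks | 9-point agreement | partial reduction | none named |
| Reduced outdoor activity, alert questionnaires | after a real alert | yes/no/not sure | amount; indoor activity; lost versus moved elsewhere | chi-square for a real moderate episode, as behaviour change |
| Intention to reduce indoor exercise | hypothetical scenario | 9-point agreement | actual behaviour | ANCOVA, as an intention |

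Only the first row grades the amount of activity done. A yes on the third row counts as the desired response, so it cannot also serve as evidence of harm.

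**2. Window**

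The item covers 7 of 28 days: 7/28 = 25% inside, 21/28 = 75% outside. The documents do not give the number or timing of alerts. If *k* alerts fall evenly and independently over the 4 weeks, the chance that none falls in the last week is 0.75^*k*:

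- *k* = 1: 75%
- *k* = 2: 56%
- *k* = 3: 42%
- *k* = 4: 32%

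These are probabilities about alerts, not shares of lost activity. A reduction that begins in week 1 and lasts into week 4 is inside the window.

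**3. Cap**

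For weekly minutes *b* before and *p* after, the part of the loss below the cap is min(*b*, 150) − min(*p*, 150), out of *b* − *p*.

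- 400 to 160 min: (150 − 150)/(400 − 160) = 0/240 = 0%.
- 200 to 100 min: (150 − 100)/(200 − 100) = 50/100 = 50%.
- 100 to 50 min: (100 − 50)/(100 − 50) = 50/50 = 100%.

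The baseline item has the same ceiling, so baseline adjustment cannot recover what the cap hides.

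The documents do not give users' activity. The table below assumes a lognormal distribution of weekly minutes (log-SD 0.8), a lasting reduction of 20% or 50%, and equal 30-minute categories up to 150. The documents label only the ends of the scale.

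| Assumed median (min/week) | Above 150 min before reduction | Lost minutes below the cap (20% / 50% cut) | People dropping at least one category (20% / 50% cut) |
|---|---|---|---|
| 60 | 12% | 69% / 76% | 40% / 78% |
| 100 | 31% | 44% / 54% | 45% / 85% |
| 150 | 50% | 25% / 34% | 40% / 79% |
| 200 | 64% | 15% / 23% | 34% / 68% |
| 300 | 81% | 6% / 11% | 22% / 50% |

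**4. Both limits together**

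If the loss is equal in each of the 4 weeks and only week-4 minutes below the cap are counted, the captured share is 0.25 times the third column: from 0.25 × 6% ≈ 2% to 0.25 × 76% = 19%. This counts minutes and is not a chance of detection. A steady loss would still show as a lower week-4 score in many people.

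**5. What a comparison would deliver**

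If 240 is the 20% inflation of the required number, 240/1.2 = 200 complete. With equal arms (assumed) of 100, the 95% half-width for a mean difference is about 1.96 × SD × √(2/100) = 0.28 SD before baseline adjustment. That could exclude a large fall in activity, but not a small one.

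**The case against.** Four points on the other side deserve weight.

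**Other measures exist.** A reader might infer that this item is the trial's only measure of lost activity. The documents do not support that. The alert-period item can record a cut in outdoor activity in weeks 1 to 3, and the cessation item looks back 4 weeks. This stands, and it confines the point to graded amount and partial loss.

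**The unseen share is unknown.** A reader might also infer that 75% of lost activity, or most of it, is invisible. That would need evenly spread alerts whose effects end before the last week, or a very active user base. The documents state none of these, and under the assumptions above most of a lasting loss lies below the cap when the median is 60 minutes a week.

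**The item may serve another purpose.** It is anchored to the NHS recommendation, no research question in section 4 concerns total activity, and someone who falls from 400 to 160 minutes still meets the recommendation. As a guideline check the scale is reasonable. But section 6.1 plans no between-arm comparison even of that, nor of the items the protocol itself labels as unwanted consequences.

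**The contrast between arms is limited.** The enhanced Moderate message to the general public opens with the same reassurance as the usual one. The enhanced High message to that group says there is no need to stay indoors. The enhanced texts offer changes of route, place or time, and Table 3 points users to parks. In the other five cells the usual messages also advise less activity, or considering it. The net effect on exercise could therefore be small or even favourable. That lowers the expected harm, but it also means the direction has to be measured.

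**Conclusion.** The point holds as a design and analysis gap that should be closed. The part that needs no assumption is this: the only graded measure of activity done covers one week of four, cannot register change above 150 minutes at either time point, and is not compared between arms in section 6.1; nor are the unwanted-consequences items. Partial losses that stay above 150 minutes, or that occur in weeks 1 to 3 and have recovered by week 4, are poorly captured by the set of items as a whole.

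The size cannot be fixed. The share of a lasting loss that lies below the cap runs from 6% to 76% over the assumed distributions, and what the window misses depends on alert timing and persistence. Sustained losses among people at or below 150 minutes, and falls from above to below that level, remain visible. The missing analysis is the firmest part, since it depends on none of these quantities.

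**What to change.** 1. **Scale.** Add response categories above 150 minutes to the activity item in both the first and the final questionnaire. While editing, check the footnote on the final item: it carries two markers, and one leads to the answer options for alert recall.
2. **Section 6.1.** Add a between-arm ANCOVA of week-4 physical activity, adjusted for baseline activity and target population, and a between-arm comparison of the unwanted-consequences items. Report each with its confidence interval as an unintended-effect outcome. The trial was not sized for these, so the interval matters more than the test.
3. **Optional.** To catch transient losses, add one graded question on total activity, indoor and outdoor, to the existing alert-period questionnaire. This is preferable to rewording the last-week item to a typical week, which would smooth over a one-week dip and give up some recall precision.

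The cost is a few extra response options, possibly one extra question, and a little more analysis. Steps 1 and 2 add no question and no visit.
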